A Phase 1 Trial of CD25/Treg-depleted DLI Plus Ipilimumab for Myeloid Disease Relapse After Matched-HCT

NCT Number: NCT03912064

IRB Approval Date: Version 5.0 Protocol Version Date 06/26/2023

NCI Protocol #: N/A

DF/HCC Protocol #: 19-142

TITLE: A phase 1 trial of CD25/Treg-depleted DLI plus Ipilimumab for myeloid disease relapse after matched-HCT

Coordinating Center: Dana-Farber Cancer Institute

Principal Investigator (PI): [name], DPhil
Dana Farber Cancer Institute
[name]
[name]
[REDACTED]

Other Investigators:

[name]

Laboratory Investigator: [REDACTED]

Study Statistician: [REDACTED]

IND #: 18510.0

IND Sponsor: [name] DPhil

Protocol Type / Version # / Version Date: Original, Version 5.0, June 26, 2023

CONFIDENTIAL

This document is confidential. Do not disclose or use except as authorized.

[figure not shown]
SCHEMA

Patient Eligibility:

[figure not shown]
- AML, MDS and MPN patients ≥ 18 years and relapsed ≥ 2 months after matched-HCT
- Adequate organ function and performance status
- No active GVHD, not on any systemic immune-suppression
- No uncontrolled active infection
- $>20\%$ T cell donor chimerism in the 4 weeks prior to cell infusion
- $<50\%$ BM involvement (% cellularity) in the 4 weeks prior to cell infusion

Treatment/Assessments:

Donor: 1-2 days prior to infusion

Recipient

Trial design: Phase 1A:

Level +2: CD25/Treg-depleted DLI 3×10^7 CD3 $^+$ cells/kg + Ipi 10 mg/kg (n up to 5)

\uparrow ($\leq 1/5$ DLT: MTD)

Level +1: CD25/Treg-depleted DLI 3×10^7 CD3 $^+$ cells/kg + Ipi 3 mg/kg (n up to 5)

\uparrow ($\leq 1/5$ DLT: dose-escalate)

Level 0: CD25/Treg-depleted DLI 3×10^7 CD3 $^+$ cells/kg + Ipi 1 mg/kg (n up to 5) (Starting Dose)

\downarrow ($\geq 2/5$ DLT: dose-de-escalate)

Level -1: CD25/Treg-depleted DLI 1×10^7 CD3 $^+$ cells/kg + Ipi 1 mg/kg (n up to 5)

Phase 1B: Additional 10 pts treated at MTD CD25/Treg-depleted DLI + Ipilimumab

CONFIDENTIAL

This document is confidential. Do not disclose or use except as authorized.

TABLE OF CONTENTS

SCHEMA.....	2
1. OBJECTIVES	5
1.1 Study Design	5
1.2 Primary Objectives.....	5
1.3 Secondary Objectives.....	5
1.4 Correlative Objectives	5
2. BACKGROUND	6
2.1 Introduction.....	6
2.2 IND Agents	7
2.3 Rationale	9
2.4 Correlative Studies Background	9
3. PARTICIPANT SELECTION.....	10
3.1 Eligibility Criteria	10
3.2 Exclusion Criteria	11
3.3 Inclusion of Women and Minorities	12
4. REGISTRATION	12
4.1 General Guidelines for DF/HCC Institutions	12

1. OBJECTIVES

1.1 Study Design:

This is an open-label, single-center Phase 1 study of CD25/Treg-depleted donor lymphocyte infusion (DLI) plus Ipilimumab in patients with AML, MDS, MPN who relapse after 8/8 HLA-matched hematopoietic cell transplantation (matched-HCT). Four dose levels combinations of CD25/Treg-depleted DLI plus Ipilimumab will be considered, starting at 3×10^7 CD3⁺ cells/kg and 1 mg/kg Ipilimumab. Cells will be infused on Day 1 and Ipilimumab will be administered every 3 weeks for 4 doses (days 1, 22, 43, and 64). Maintenance Ipilimumab every 3 months for 4 doses will be administered at weeks 24, 36, 48 and 60, to patients without disease progression at the day 92 (end of week 13) response assessment.

1.2 Primary Objectives

To determine the safety (MTD) of CD25/Treg-depleted DLI plus Ipilimumab in patients with myeloid relapse after matched-HCT.

1.3 Secondary Objectives

1. To determine complete remission (CR/CRi) rate at day 43 (6 weeks).
2. To determine the rate of progression-free survival (PFS) and overall survival (OS) at ~3 months (day 92) and ~1 year (week 60) post cell infusion.
3. To determine the ~3 month (day 92) incidence and severity of acute GVHD rates after cell infusion.
4. To determine the ~1 year (week 60) incidence and severity of chronic GVHD rates after cell infusion.

1.4 Correlative Objectives

1. To assess the immunologic impact of infusions of CD25/Treg-depleted DLI plus Ipilimumab. These include immunophenotypic analysis of T-cell subsets, B and NK cells; phenotypic and functional readouts of effector T (Teff) and regulatory T (Treg) cell activation status; changes in plasma cytokines and chemokines; tumor microenvironment; and tumor mutation profile.
2. To correlate clinical response with changes in circulating Teff vs. Treg cell counts and activation; the persistence of adoptively transferred Teff cells; changes in cytokine and chemokine levels; tumor infiltration by activated CD8⁺ T cells; and tumor mutation profile, blast phenotype and tumor microenvironment.
3. In an exploratory analysis, to perform tumor neoantigen discovery to identify novel T cell targets and correlate tumor mutational load with response.

CONFIDENTIAL

This document is confidential. Do not disclose or use except as authorized.

2. BACKGROUND

2.1 Introduction

For many patients with myeloid malignancies (e.g. acute myeloid leukemia (AML), myelodysplastic syndromes (MDS), and myeloproliferative neoplasms (MPN)), allogeneic hematopoietic cell transplantation (HCT) offers the only opportunity for cure. Unfortunately, myeloid disease relapse after transplant is associated with dismal outcomes, and remains a major obstacle to HCT success¹. Currently, up to 40% of patients with AML/MDS undergoing HLA-matched related or unrelated HCT (matched-HCT) relapse^{2,3}. HCT relapses are usually treated by withdrawal of IS, chemotherapy for interim disease control, and/or donor lymphocyte infusion (DLI) to invoke potentially curative graft-versus-tumor (GVT) immune responses. However, AML/MDS remissions after DLI are infrequent and short-lived, with poor patient survivals typically measured in months^{4,5}. Clinical graft-versus-host-disease (GVHD) toxicity is common after DLI. Innovative approaches to enhance anti-tumor immune responses are urgently needed.

Immune escape (i.e. tumor evasion of the donor immune system) contributes to myeloid disease relapse after allogeneic HCT. In HLA-matched HCT, presentation of host hematopoietic and/or tumor epitopes within the concordant HLA context can invoke T cell receptor (TCR)-mediated recognition and elimination by donor-derived effector T (Teff) cells and induce curative GVT responses, a process that may be antagonized by suppression of co-stimulatory immune pathways, inhibitory regulatory T (Treg) cells, or by activation of inhibitory immune checkpoint pathways⁶⁻⁸.

We therefore hypothesized that Treg cells in the DLI product could suppress GVT, and selective depletion of CD25^{hi} cells (including constitutive CD25^{hi} Treg cells) from the DLI product could boost its clinical efficacy, if severe clinical GVHD was avoided. In a phase 1 study we manufactured CD25/Treg-depleted DLI (via ClinMACS CD25 reagent system, Miltenyi Biotec GmbH), documenting its safety and promising efficacy at a dose of 3×10^7 CD3⁺ T cells/kg, highlighting complete durable remissions in relapsed AML/MDS⁹.

We additionally hypothesized that blockade of the inhibitory CTLA-4 immune checkpoint with Ipilimumab Ipi may induce a GVT effect in patients in relapse after HCT. In a phase 1 trial of Ipilimumab monotherapy for patients with relapsed hematologic malignancies including AML/MDS after HCT, we documented the feasibility, safety and promising early efficacy of CTLA-4 blockade, including some complete durable remissions in patients with myeloid disease¹⁰. Response was associated with increased tumor infiltration of perforin-expressing Teff cells, and fewer circulating Treg cells.

We now propose to leverage our prior experience and combine CD25/Treg-depleted DLI with CTLA-4 blockade via Ipilimumab to maximally augment Teff activity while avoiding infusion of suppressive Treg cells. We hypothesize that such combination therapy will enhance the efficacy of DLI in patients with myeloid disease relapse after matched-HCT.

CONFIDENTIAL

This document is confidential. Do not disclose or use except as authorized.

2.2 IND Agents

2.2.1 CD25/Treg-depleted DLI for matched HCT relapse

Tregs are $CD4^+CD25^{hi}Foxp3^+$ lymphocytes that comprise approximately 5-10% of the circulating $CD4^+$ T cell population, that act to dominantly suppress autoreactive lymphocytes, and control innate and adaptive immune responses¹¹⁻¹⁸. In murine studies, transfer of $CD4^+$ T cells depleted of Tregs induces autoimmunity, while transfer of $CD4^+$ Tregs is protective^{19,20}. Patients with systemic lupus erythematosus, rheumatoid arthritis, and multiple sclerosis exhibit deficiencies in Treg number and function²¹⁻²³. The relationship between Tregs and autoimmunity prompted interest in their potential role in GVHD. Adoptive transfer of donor Treg at HCT can prevent or mitigate GVHD in animal models²⁴⁻²⁶. Several groups examined the PB of patients at various stages after HCT and found that the number of circulating Tregs inversely correlated with GVHD²⁷⁻³⁰. We previously reported that in-vivo Treg enhancement with daily subcutaneous (SC) low-dose interleukin-2 (IL-2) therapy can induce clinical responses in steroid-refractory chronic GVHD^{31,32}. Tregs can also potentially suppress the GVT response. In vitro Tregs suppress proliferation of $CD4^+$ and $CD8^+$ Teff cells after polyclonal or antigenic stimulation¹⁷. In vivo Tregs diminish immune responses to solid and liquid tumors, including AML³³⁻³⁶. We therefore hypothesized that selective depletion of Tregs (by depletion of $CD25^{hi}$ cells) from the DLI product could boost its clinical efficacy, if severe clinical GVHD was avoided.

[figure not shown]

Fig 1: Flow Cytometric Analysis of $CD4^+CD25^+FoxP3^+$ Cells Confirms Treg Depletion. The initial apheresis product (top plots) and CD25-depleted target fraction (bottom plots) indicate reduction in $CD25^{hi}$ cells (left)

In a phase 1 study for patients with disease relapse after matched-HCT, we evaluated the feasibility of manufacturing Treg depleted DLI products as well as the safety and potential efficacy of these cells. Treg depleted DLI products were obtained by depleted $CD25^{hi}$ cells from donor apheresis products using antibody-conjugated magnetic beads (Miltenyi Biotech – CliniMacs)⁹. Sixteen of 21 subjects received prior cytoreductive therapy, but only four were in complete remission at time of infusion. Two DLI dose levels were administered: 1×10^7 (n=6) and 3×10^7 $CD3^+$ cells/kg (n=15). A median 2.3 log-depletion of $CD4^+CD25^{hi}FOXP3^+$ Treg cells was achieved in the released product (Fig. 1).

Infusion of CD25/Treg-depleted products was not associated with acute toxicity. Seven subjects (33%) developed clinically significant GVHD by one year, including one fatal case. At Dose Level 1, five treated patients demonstrated progression, while one patient had stable disease. At Dose Level 2 however, nine subjects (60%) achieved responses (8 CR, 1 PR), including seven who had active disease at time of DLI. One-year survival was 53%. When compared to unmodified DLI in contemporaneous patients meeting study eligibility (n=14), CD25/Treg-depleted DLI at dose-level 2 was associated with an improved response rate (60% vs. 14%, p=0.02) and 1-year event-free survival (EFS, 27% vs. 0%, p=0.0075, Fig. 2), with a reduction in

CONFIDENTIAL

This document is confidential. Do not disclose or use except as authorized.

relapse incidence (67% vs. 100%, $p=0.002$), and no increase in non-relapse mortality (NRM). Importantly four of 8 (50%) subjects with AML relapse remained in remission at 1 year.

In correlative analyses, while significant shifts within the naïve and memory T compartments of circulating CD4 $^{+}$ T cells were observed at 1 and 2 months after CD25/Treg-depleted DLI, no differences were observed between responder and non-responder populations, perhaps due to limited sample size. While these results are promising, strategies to further enhance curative GVT responses by optimizing Teff activation (e.g., via CTLA-4 blockade as indicated below) are attractive.

2.2.2 Ipilimumab for post HCT relapse

The engagement of cytotoxic T-lymphocyte-associated protein 4 (CTLA-4) and programmed death 1 (PD-1) receptors by their ligands B7-1/2 and PD-L1/2 respectively inhibits Teff function. Tumor cells often express these inhibitory ligands, thereby selectively blocking antitumor immunity. In murine models, PD-1 blockade led to an increase in GVHD, whereas selective blockade of CTLA-4 to treat late relapses after transplantation augmented GVT effects without accelerating GVHD^{37,38}. We hypothesized that CTLA-4 blockade with Ipilimumab may induce a GVT effect in patients in relapse after HCT.

In a phase 1 study of Ipilimumab dosed at 3 and 10 mg/kg, we evaluated its safety and potential efficacy in 28 patients with relapsed hematologic malignancies post-transplant (12 AML patients, including 3 with leukemia cutis and 1 with myeloid sarcoma; and 2 patients with MDS)¹⁰. At the 10 mg/kg dose-level, Ipilimumab dose-limiting toxicity (DLT) included two cases of chronic GVHD of the liver and one case of grade II acute GVHD of the gut, all of which resolved with steroids but precluded further Ipilimumab administration. One patient died 42 days after initial dose of Ipilimumab, after grade 3 colitis and grade 4 pneumonitis developed. In the 3 mg/kg cohort, no responses were noted, but one patient with extramedullary AML of the breast had a tumor flare after two doses of Ipilimumab, and then a 27% decrease in the size of the mass at the end of Ipilimumab induction, maintained for 12 additional weeks. In the 10 mg/kg cohort, 7 of 22 patients (32%) had a response; 5 patients (23%) with a complete response (CR), including all 3 patients with leukemia cutis (**Fig. 3**), 1 with myeloid sarcoma involving lymph nodes, and 1 with MDS developing into AML. Four patients who had a response continued to have a durable remission for more than 1 year. In

[figure not shown]

Fig 2: Clinical Outcomes after CD25/Treg-depleted DLI (dose-level 2). 1-year EFS benefit for Treg-depleted DLI (27%) vs. Unmanipulated DLI (0%).

[figure not shown]

Fig 3: Clinical and Histopathological Responses to Ipilimumab in a Patient with Leukemia Cutis.

unpublished data, 5 mg/kg Ipilimumab dose appears less effective than 10 mg/kg, with similar toxicity. While promising, these data indicate a need for further enhancement of GVT beyond that obtained with Ipilimumab alone.

Exploratory immunohistochemical and gene-expression data indicated that in leukemia cutis, Ipilimumab therapy drove infiltration of cytotoxic CD8⁺ T cells to the site of disease both in responders and non-responders, but CD8⁺ T-cell perforin-1 up-regulation was more apparent in two responders compared to non-responders. PB analysis showed decreased circulating CD4⁺ Tregs and increased CD4⁺ Teff cells in patients who had a response. Moreover, in responders the proportion of activated CD4⁺ Treg cells was less than in non-responders. These observations suggest that CTLA-4 blockade may be effective after allogeneic HCT by inducing an intratumoral GVT response, but that responses might be blunted by Tregs. Strategies to avoid infusing Tregs while de-repressing Teff cells might therefore help to further enhance therapeutic GVT responses.

2.3 Rationale

Based on the initial safety and promising efficacy observed in our phase 1 trials of CD25/Treg-depleted DLI and Ipilimumab individually, we hypothesize that combination therapy will be safe in patients with AML, MDS and MPN who relapse after matched-HCT and provide an enhanced curative effect for these patients with otherwise extremely poor prognosis.

2.4 Correlative Studies Background

Clinical trial administration of adoptively transferred CD25/Treg-depleted DLI plus Ipilimumab provides a unique opportunity to study their biology within patients. Peripheral blood (PB), bone marrow (BM) and accessible extramedullary disease site biopsy (e.g. leukemia cutis, if applicable) samples obtained before (at baseline), during, and after therapy (e.g. landmark time points like Day +30, Day +100 etc.,) and at the time of relapse (if any) will be obtained to assess the immunologic effects of treatment.

Viable cells as well as plasma will be isolated and cryopreserved at each time point using validated lab SOPs. Since all patients will have active relapse at the initiation of therapy, baseline samples will have tumor cells as well as normal donor immune cells. We will conduct detailed immunologic and tumor assessments, characterizing immune cells pre- and post-treatment, evaluating their functional activity, and assessing the tumor microenvironment to identify biologic predictors of response. We hypothesize that infusion of DLI preferentially depleted of Treg cells in combination with Ipilimumab will result in enhanced GVT mediated by donor Teff cells. To examine this hypothesis, correlative studies will use multiple orthogonal approaches to monitor changes in T cell activation, T cell specificity and T cell function in responders and non-responders. *Specifically, we will seek to correlate clinical response with 1) changes in circulating Teff vs. Treg cell counts and activation status via flow cytometry and mass cytometric analysis; 2) the persistence of adoptively transferred Teff cells via TCR sequencing; 3) changes in cytokine and chemokine levels; 4) tumor infiltration by activated CD8⁺ T cells; and 5) tumor mutation profile, blast phenotype and tumor microenvironment via unbiased single-cell expression profiling of the immune microenvironment (e.g. CD8⁺ T, CD4⁺ Teff, CD4⁺ Treg, NK, B, DC, Macrophage, MDSC, blast cells) using specialized microfluidic platforms (e.g.*

CONFIDENTIAL

This document is confidential. Do not disclose or use except as authorized.

inDrop and 10x Genomics) we have optimized for use in cryopreserved BM, PB, and other single cell suspensions. In an exploratory analysis, we will perform tumor neoantigen discovery to identify novel T cell targets and correlate tumor mutational load with response.

3. PARTICIPANT SELECTION

3.1 Eligibility Criteria

3.1.1 Histologically or cytologically or molecularly confirmed relapse of AML, MDS or MPN including ***CML, myelofibrosis or MDS/MPN***. Disease relapse includes patients with myeloid blasts by flow and/or morphology in marrow or extramedullary disease sites; or persistence and/or recurrence of disease defining mutations.

3.1.2 Relapse at ≥ 2 months after any 8/8 or better HLA-matched HCT

3.1.3 Available original stem cell donor.

3.1.4 Age ≥ 18 years. Because no dosing or adverse event data are currently available on the use of Ipilimumab in participants <18 years of age, children are excluded from this study.

3.1.5 ECOG performance status ≤ 2 (Karnofsky performance status ≥ 60 , see **Appendix A**).

3.1.6 Recipient donor T cell chimerism $\geq 20\%$ within 4 weeks prior to cell infusion.

3.1.7 $<50\%$ bone marrow involvement within 4 weeks prior to cell infusion.

3.1.8 No systemic corticosteroid therapy for GVHD (≤ 5 mg of prednisone or equivalent doses of other systemic steroids for non-GVHD, non-autoimmune indications for at least 4 weeks prior to cell infusion).

3.1.9 No other systemic medications/treatments (e.g. ECP) for GVHD for at least 4 weeks prior to cell infusion.

3.1.10 Ability to understand and willingness to sign written informed consents.

3.1.11 Adequate organ function as defined below:

- Total bilirubin: $\leq 1.5 \times$ institutional upper limit of normal (ULN) (except Gilbert's or disease-related hemolysis, then $< 3 \times$ ULN)
- AST(SGOT)/ALT(SGPT): $\leq 3 \times$ institutional ULN
- creatinine clearance: $\leq 1.5 \times$ institutional ULN
- O₂ saturation: $\geq 90\%$ on room air
- LVEF $> 40\%$

CONFIDENTIAL

This document is confidential. Do not disclose or use except as authorized.

3.1.12 The effects of CD25/Treg-depleted DLI and Ipilimumab on the developing human fetus are unknown. For this reason and because immunomodulatory agents are known to be teratogenic, women of child-bearing potential and men must agree to use adequate contraception (hormonal or barrier method of birth control; abstinence) prior to study entry and for the duration of study participation. Should a woman become pregnant or suspect she is pregnant while participating in this study or within 23 weeks after the last dose of study drug, she should inform her treating physician immediately. Men treated or enrolled on this protocol must also agree to use adequate contraception prior to the study, for the duration of study participation, and for at least 31 weeks after completion of Ipilimumab administration.

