5.2 Pre-Treatment Criteria

5.2.1 Cycle 1, Day 1

In order to start on therapy, subjects must meet all of the inclusion criteria outlined in Section 3.1, and must not have any of the exclusion criteria outlined in Section 3.2.

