Serum Chemistry ⁵	X	X	X	X	X	X	X	X	X	X	X
TSH											X
Chimerism testing		X									X
PB Correlative studies ⁶	X	X ¹²			X ¹²			X			X ¹²
BM aspirate and core ⁷		X			X						X
aGVHD assessment ⁸	X	X	X	X	X	X		X	X	X	X
cGVHD assessment ⁹		X			X			X			X

CONFIDENTIAL

This document is confidential. Do not disclose or use except as authorized.

- * – Patients will be dosed at start of week 1, 4, 7, and 10 (induction) and return for an end of induction response evaluation on start of week 14. Maintenance dosing will then occur at weeks 24, 36, 48 and 60. Patients who experience clinical benefit may continue to receive Ipilimumab q12 weeks till week 60 unless there is unacceptable toxicity, disease progression, or withdrawal of consent.
- **– End of study off-treatment visit will be 3 months after last dose of maintenance Ipilimumab. Note: for IND/IDE trials, follow up visits or other contact are required in order to identify SAEs during the 30 days following the end of study treatment
- 1 – A baseline EKG and cardiac ECHO (or MUGA) is required for all patients, and anytime thereafter as clinically indicated.
- 2 – For those with evidence of CHF, myocardial infarction, myocarditis or cardiomyopathy at any time during the study, a detailed cardiac evaluation including labs (CPK, Troponin), cardiology consult, with EKG and ECHO (or MUGA) at minimum is required, as clinically indicated. Please refer to **Section 6.1.13** for guidance on cardiac toxicity management for Ipilimumab.
- 3 – For females of childbearing potential only
- 4 – O_2 Saturation on room air required only at screening; Weight on day closest prior to infusion will be used for study dosing calculations, height only needs to be collected at screening.
- 5 – Includes: comprehensive metabolic panel, LFTs, magnesium, phosphorus, uric acid, LDH, lipase, eGFR
- 6 – See **Section 9.1.1**.
- 7 – See **Section 9.1.2 and 9.1.3**. If there is no bone marrow involvement at baseline and/or extra-medullary disease is documented, the other sites of disease relapse will be assessed as clinically appropriate (**section 9.1.3** e.g. measurement of lesions of leukemia cutis including skin biopsy, PET/CT assessments for other extramedullary sites (e.g. granulocytic sarcoma)
- 8 – See **Appendix C** for aGVHD assessment
- 9 – Per NIH consensus criteria for cGVHD assessment
- 10 – Viral Panel includes HIV, Hep B and C
- 11 – Exception under 9.1.1 a). Draw a PASQ6P
- 12 – Exception under 9.1.1 b). Draw a PASQ4P

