Appendix B: BODY SURFACE AREA AND CREATININE CLEARANCE

Body surface area (BSA) should be calculated using Dubois formula that yields the following results in meters squared (m²):

$$\text{BSA} = (W^{0.425} \times H^{0.725}) \times 0.007184$$

where the weight is in kilograms and the height is in centimeters.

Creatinine clearance (CrCl) can be calculated using the Cockcroft-Gault equation as follows:

$$\text{CrCl (ml/min)} = \frac{(140 - \text{age}) (\text{actual wt in kg})}{72 \times \text{serum creatinine (mg/dl)}}$$

For females, use 85% of calculated CrCl value.

Note: In markedly obese participants, the Cockcroft-Gault formula will tend to overestimate the creatinine clearance. (Adipose tissue tends to contribute little creatinine requiring renal clearance.)

CONFIDENTIAL

This document is confidential. Do not disclose or use except as authorized.

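### Section 3.1.11 puts a ceiling, not a floor, on creatinine clearance, so the renal criterion screens out nobody for poor renal function

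*Combined protocol and SAP*

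**What the plan says.** Section 3.1.11 opens its list with "Adequate organ function as defined below" and gives the renal entry as "creatinine clearance: $\leq 1.5 \times$ institutional ULN". The entries around it set their limits in the direction that fits the measure. Bilirubin, where a high value is bad, has an upper limit ("Total bilirubin: $\leq 1.5 \times$ institutional upper limit of normal (ULN"), and so do the transaminases. Oxygen saturation, where a low value is bad, has a lower limit ("saturation: $\geq 90\%$ on room air"), and so does LVEF.

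Appendix B gives a way to obtain clearance: "Creatinine clearance (CrCl) can be calculated using the Cockcroft-Gault equation as follows". The result is in ml/min, serum creatinine is in the denominator, and there is a sex adjustment: "For females, use 85% of calculated CrCl value".

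The list is not advisory. Section 5.2.1 states: "In order to start on therapy, subjects must meet all of the inclusion criteria outlined in Section 3.1". Under Section 4.1 an investigator confirms eligibility and the study team completes a protocol-specific checklist.

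The only other renal measurement in the screening schedule is in the chemistry panel defined in footnote 5 of the study calendar (Section 10): "Includes: comprehensive metabolic panel, LFTs, magnesium, phosphorus, uric acid, LDH, lipase, eGFR". No eligibility cut-off is attached to the eGFR.

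**The concern.** For clearance, the dangerous direction is down. A limit that says only how high clearance may be accepts every patient whose clearance is low. The measure named and the direction of the inequality do not fit each other, and on the kidney the organ-function screen does not do what its heading promises.

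Two things are at stake. The first is patient safety and consistent screening. Staff who follow the text admit patients with renal impairment; staff who follow common sense apply a limit that the protocol does not contain. The second is the reading of toxicity. The protocol lists kidney failure among ipilimumab risks (7.2.1.2) and mentions immune-related nephritis (6.1.13). Under item 1 of Section 5.4, a grade 4 or persistent grade 3 non-hematologic event at least possibly related to treatment is a DLT, with GVHD and immune-related events handled separately. The exemption there for brief metabolic abnormalities names blood urea nitrogen but not creatinine. When renal function worsens in a patient whose impaired baseline was never screened, the relatedness judgement is harder. Small counts drive the decisions: two DLTs in a cohort of up to five exceed the MTD (5.1.5, 13.4), and three in the ten expansion patients halt accrual (13.4).

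**Working it through.** The plan states no figure for this criterion, so there is nothing to reproduce. The check is one of direction, illustrated with the plan's own formula.

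**Inputs.** The criterion (3.1.11): CrCl ≤ 1.5 × ULN. The formula (Appendix B): CrCl = (140 − age) × weight / (72 × SCr), multiplied by 0.85 for females, with SCr in mg/dl. The documents give no institutional ULN for clearance, so 100, 120 and 140 ml/min are assumed, which makes the caps 150, 180 and 210 ml/min. The patients are hypothetical.

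**Step 1: direction.** Putting the formula into the criterion and solving for serum creatinine gives

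SCr ≥ (140 − age) × weight / (72 × 1.5 × ULN).

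A ceiling on clearance is therefore a floor on serum creatinine. For a man aged 60 weighing 70 kg the numerator over 72 is 80 × 70 / 72 = 77.8. The criterion would exclude him only if his creatinine were below 77.8/150 = 0.52, 77.8/180 = 0.43 or 77.8/210 = 0.37 mg/dl, depending on the assumed ULN. Rising creatinine never excludes him.

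**Step 2: patients with falling function.** Age 60, 70 kg:

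| SCr (mg/dl) | Man, CrCl (ml/min) | Woman, CrCl (ml/min) | Meets the criterion at all three caps |
|---|---|---|---|
| 1.0 | 77.8 | 66.1 | yes |
| 2.0 | 38.9 | 33.1 | yes |
| 4.0 | 19.4 | 16.5 | yes |
| 5.0 | 15.6 | 13.2 | yes |
| 8.0 | 9.7 | 8.3 | yes |

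For example, the man at 5 mg/dl: (140 − 60) × 70 / (72 × 5) = 5600/360 = 15.6. The woman: 15.6 × 0.85 = 13.2.

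**Step 3: who fails.** A man aged 30 weighing 100 kg with creatinine 0.7 mg/dl has 110 × 100 / (72 × 0.7) = 218.3 ml/min, above all three caps. He is ineligible on the renal line although his calculated clearance is the highest shown here. With creatinine 1.0 mg/dl he has 152.8 ml/min, which fails at an assumed ULN of 100 and passes at 120 and 140.

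**Step 4: dependence on the assumed ULN.** The ULN decides which high values are excluded. It does not affect the conclusion for low values: any clearance at or below the ULN is below 1.5 × ULN.

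**Step 5: is there a renal limit elsewhere?**
- The schema asks only for adequate organ function in general terms.
- The exclusion for uncontrolled intercurrent illness (3.1.22) is open-ended, but names no renal condition or value.
- Section 6.1.6 requires laboratory results to be reviewed and in range before ipilimumab, but states no renal range.
- The study calendar collects eGFR without a threshold.

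None of these supplies the missing floor.

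**The case against.** The best defence is that this is an obvious slip. The form of the limit is that of the bilirubin entry and would suit a measure where high values are bad, such as serum creatinine. A transplant investigator is unlikely to apply it as a cap on good function. Section 3.1.11 does not cite Appendix B, whereas 3.1.5 does cite Appendix A, and Appendix B offers its formula as something that can be used. Chemistries including eGFR are taken at screening and should be repeated within a week of starting, so a patient with creatinine 5 mg/dl would not reach dosing unseen.

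Much of that stands. The provisions in 3.1.22 and 6.1.6 could stop an individual patient. But they work by judgement, and the documents do not say which measure was intended. A binding criterion that is safe only when staff depart from its wording still needs correcting. Nor does the direction problem rest on Appendix B: clearance is higher when function is better, however it is obtained.

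A reader might infer more than the documents support:
- **That sites will screen differently.** The study is single-center (1.1, 13.1), and the sections for other investigative sites (4.3, 4.4) are marked not applicable. Other centers appear only for donor evaluation and apheresis (5.1.2). What remains possible is variation between the people who screen.
- **That baseline impairment itself will be counted as toxicity.** Section 7.1.1 defines an adverse event as something that develops or worsens after treatment or a protocol procedure begins, so stable impairment is not one. A DLT under item 1 of Section 5.4 also needs the stated severity and at least possible relatedness. Only worsening from an impaired baseline is affected.
- **That patients with renal failure were enrolled, or that the MTD decision was affected.** Nothing in the documents shows either.

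**Conclusion.** The criterion is wrong as written. It has no floor at any level of clearance, and this holds whatever the institutional ULN, because low clearance always satisfies the inequality. In the illustration, clearances from 77.8 down to 9.7 ml/min all pass, and the patient excluded at every assumed cap has 218.3 ml/min. The assumed ULN range of 100 to 140 ml/min affects only where high values are cut off.

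The consequence is limited but real. A binding safety screen is left to unwritten judgement for one organ, and renal worsening in a patient with an unscreened impaired baseline would be harder to attribute in the DLT assessment. This is an error in the eligibility wording. It changes no endpoint, sample size, escalation rule or operating characteristic.

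**What to change.** Amend the renal entry in Section 3.1.11 so that the named measure and the direction of the limit agree with each other and with Appendix B. Two forms would do this: serum creatinine with an upper limit, or creatinine clearance by Appendix B, in ml/min, with a lower limit. The sponsor chooses the measure and the value; none is proposed here. If clearance is kept, cite Appendix B in the criterion so that the method of calculation is fixed.

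Then check that the protocol-specific eligibility checklist matches. The checklist is not part of the documents and may already be right.

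The cost is a one-line amendment and, if needed, an updated checklist. No statistical section has to be reworked.
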